Short-term Effects of Intravenous Dexketoprofen Trometamol and Tramadol on Perfusion-Related Physiological Parameters in Renal Colic

Short-term Perfusion Effects: Dexketoprofen/Tramadol

METHODS

Study design and setting

This single-centre, prospective, randomised study was conducted in the emergency department of Ataturk University Research and Training Hospital between November 2024 and April 2025. Adult patients aged 18–55 years presenting with flank pain and diagnosed with renal colic based on clinical evaluation and appropriate imaging were screened for eligibility.

Participants

Patients who met the inclusion criteria were required to have a Glasgow Coma Scale score of 15, spontaneous respiration, and the capacity to provide informed consent. Exclusion criteria encompassed pregnancy or breastfeeding, chronic kidney disease, known allergy to study medications, chronic respiratory disease, hemodynamic instability, acute intoxication, uncontrolled epilepsy, or recent monoamine oxidase inhibitor use.

Randomisation and interventions

Participants were randomly assigned to one of three groups in a 1:1:1 ratio, receiving intravenous dexketoprofen trometamol (50 mg), tramadol (100 mg), or a combination of dexketoprofen trometamol (50 mg) and tramadol (50 mg). All medications were diluted in 100 mL of normal saline and administered intravenously. The administration of rescue analgesia in the form of intravenous morphine (5 mg) was permitted at the discretion of the treating physician.

Data collection and monitoring

Physiological variables, including blood pressure, heart rate, oxygen saturation, respiratory rate, and EtCO₂, were recorded at baseline (T0), 30 minutes (T30), and 60 minutes (T60). Arterial blood-gas analysis was performed at T0 and T60. The primary outcome of the study was a change in EtCO₂ over time, while secondary outcomes included changes in vital signs and blood-gas parameters.

The primary outcome was the change in EtCO₂ over time (T0, T30, T60) and the comparison of these changes between the three analgesic groups as a surrogate marker of global tissue perfusion. Secondary outcomes encompassed the trajectories of heart rate, blood pressure and SpO₂ over time; changes in arterial blood gas parameters (pH, bicarbonate, PaCO₂, lactate and

base deficit) between T0 and T60; and comparison of these physiological responses across treatment groups.

Sample size and statistical analysis

Sample size was calculated in G*Power using previously published data on EtCO₂ changes after tramadol or oxycodone administration (16). With $\alpha = 0.05$ and 80% power, 34 patients per group (102 in total) were required.

The analysis of the data was conducted utilising the SPSS version 25.0 software. The assessment of normality was conducted through histogram inspection and the implementation of the Shapiro–Wilk test. Continuous variables are presented as mean \pm standard deviation or change over time, and categorical variables as counts and percentages. The alterations in vital signs and blood-gas variables occurring within and between the groups were subjected to analysis using repeated-measures ANOVA. For the purpose of comparing the between-group alterations, one-way ANOVA with Tukey post hoc tests were employed. Paired t tests were utilised for within-group comparisons between T0 and T60, and χ^2 tests were used for the analysis of categorical variables. Statistically speaking, a p value of less than 0.05 was deemed to be significant.

Ethics Approval

The study was approved by the Erzincan Binali Yıldırım University Clinical Research Ethics Committee (Decision No. 2024-16/01, 07 Nov 2024) and conducted in accordance with the Declaration of Helsinki. All participants provided written informed consent.

CRediT authorship contribution statement

[name]: Conceptualization, Data curation, Formal analysis, Investigation, Methodology, Resources, Software.

[name]: Conceptualization, Formal analysis, Investigation, Methodology, Resources, Supervision, Validation, Visualization, Writing – original draft, Writing – review & editing.

Declaration of Competing Interest

The authors declare that they have no competing financial interests or personal relationships that could have influenced the work reported in this paper.

Data availability statement

The data that support the findings of this study are not publicly available due to privacy and ethical restrictions, as they contain identifiable patient information.

Funding Statement

No funding

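### Does the analysis need a stated rule for measurements taken after rescue morphine?

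*Combined protocol and SAP*

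**What the plan says.** Rescue is open to all three arms: "The administration of rescue analgesia in the form of intravenous morphine (5 mg) was permitted at the discretion of the treating physician". Neither a trigger nor a time window is stated.

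Under Data collection and monitoring, EtCO₂ and vital signs are read at T0, T30 and T60. For blood gases, "Arterial blood-gas analysis was performed at T0 and T60". The primary outcome is the change in EtCO₂ and "the comparison of these changes between the three analgesic groups as a surrogate marker of global tissue perfusion".

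Sample size and statistical analysis names three analyses of these values:

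- Trajectories over time, by arm: "The alterations in vital signs and blood-gas variables occurring within and between the groups were subjected to analysis using repeated-measures ANOVA"
- Contrasts of change across arms: "For the purpose of comparing the between-group alterations, one-way ANOVA with Tukey post hoc tests were employed"
- Change inside each arm: "Paired t tests were utilised for within-group comparisons between T0 and T60"

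It also provides counts, percentages and χ² tests for categorical variables, without naming them. It has no rule for post-rescue values, no analysis set and no estimand.

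**The concern.** The rescue drug is itself an active analgesic, and the primary outcome is a physiological response read at times that rescue may precede. The title promises "Short-term Effects of Intravenous Dexketoprofen Trometamol and Tramadol on Perfusion-Related Physiological Parameters in Renal Colic", which invites a reading in terms of the assigned drugs alone. If one arm needed morphine more often, part of any EtCO₂ difference between arms, or part of its absence, could come from morphine. The paired T0–T60 tests look more exposed still: they have no comparator, so a rescue effect stays in the result even when morphine use is the same in every arm. Without a stated handling or counts by arm, a reader cannot tell which of these happened.

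**Working it through.** **1. Can rescue precede an outcome value?** Yes. No timing is stated, and T30 and T60 both follow treatment. The documents do not say that any patient received morphine before T60.

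**2. What do the written tests do with such values?** No test carries a rescue term and no exclusion is written. Taken as written, each uses the recorded values by randomised arm.

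**3. The plan's own figure.** It states 34 per group (102 in total) at α = 0.05 and 80% power. This cannot be reproduced, because no effect size, SD or G*Power test is given. Solving backwards with two-sided α:

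- Normal approximation, one pair: d = (1.960 + 0.842) × √(2/34) = 0.68. The noncentral t version gives 0.69.
- One Tukey pair: critical value 3.365/√2 = 2.379 on 102 − 3 = 99 df; 80% power at d = 0.783.

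The rest of the between-arm check uses the Tukey benchmark.

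**4. Shift in a pairwise contrast.** Let r be the proportion rescued before the measurement and m the morphine shift in SD of change. Then

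shift = r₁m₁ − r₂m₂.

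With equal rates and effects, or with rescue after the measurement, the shift is 0. With the same m in both arms it is (r₁ − r₂) × m. **All values of r and m below are assumed.**

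| Rate gap × m | Shift (SD) | Power at 0.783 − shift | Power at 0.783 + shift | Rejection if there is no difference without rescue |
|---|---|---|---|---|
| none | 0 | 80% | 80% | 1.9% |
| 0.10 × 0.25 | 0.025 | 77% | 83% | 2.0% |
| 0.20 × 0.5 | 0.10 | 67% | 89% | 3.0% |
| 0.30 × 1.0 | 0.30 | 35% | 98% | 13.1% |

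These figures ignore the extra variance that arises when only some patients in an arm are rescued. Simulation including it, with 40% v 10% rescued at 1.0 SD, gives 31%, 96% and 11.8% in place of the last row.

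**5. Shift within one arm of 34.** The shift is r × m, tested by a paired t test on 33 df with no other change over time.

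| r × m | Shift (SD) | Rejection |
|---|---|---|
| none | 0 | 5% |
| 0.10 × 0.25 | 0.025 | 5.2% |
| 0.20 × 0.5 | 0.10 | 8.7% |
| 0.30 × 1.0 | 0.30 | 39.7% (33.7% with the mixed-rescue variance) |

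**6. What the figures mean.** They are departures from a target in which nobody receives morphine. If the target is assignment with rescue available, a contrast shifted by unequal rescue is a true non-zero assignment effect. Neither the lower power nor the higher rejection is then an error rate. The within-arm change already mixes drug, time and pain relief, so it would not isolate the drug even with no rescue at all.

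**7. The other possible handling.** If rescued patients had been dropped, the comparison would no longer be of the randomised groups. With an assumed 20% dropped, 34 × 0.8 ≈ 27 per arm remain, and power at d = 0.68 is Φ(0.68 × √(27/2) − 1.96) ≈ 70%. Nothing in the documents says that this was done.

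**The case for a change.** The strongest case for a change is that silence leaves more than one handling open. Keeping all values preserves the randomised comparison; dropping rescued patients does not, and it costs power. The choice is never written down. In a trial of analgesics with a physiological outcome, one sentence and one table row would settle the matter, and since the text describes a study already conducted, both are still feasible.

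What stands is that the text is silent and that a sentence would help the reader. What does not stand is the step from there to a defect in the plan. Writing the sentence alters no test, number or rule. Nor can a reviewer dictate it: the text is in the past tense, so an instruction to declare that all values were analysed as randomised would be false if they were not. The supportable request is only to say which handling was used. Morphine counts belong in a results report, and the unnamed categorical variables may already include them.

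**Conclusion.** No change to the plan. This is a gap in description that an analyst fills sensibly by keeping every patient and every value in the assigned arm. Between-arm results are then effects of assignment with rescue available, and within-arm T0–T60 results are change over time with rescue available.

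Size and direction are unknown. The range of 0 to 0.30 SD either way rests wholly on assumed rescue rates and morphine effects, and it measures harm only against a no-rescue target that the plan does not adopt. The small end is negligible, and the documents cannot show where the trial falls.

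The conclusion depends on post-rescue values having been kept, which is the natural reading but is not stated. If rescued patients or their values were dropped, the report should say so and note that the comparison is no longer of the full randomised groups. In either case, morphine use by arm before T30 and between T30 and T60 is worth reporting where charted, as a courtesy to the reader.

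### Does the missing test and effect size behind 34 patients per group call for a change to the plan?

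*Combined protocol and SAP*

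**What the plan says.** The sample-size justification in the combined protocol and SAP is two sentences long. The first gives the software and the source: "Sample size was calculated in G*Power using previously published data on EtCO₂ changes after tramadol or oxycodone administration". The second gives the result: "80% power, 34 patients per group (102 in total) were required", at alpha 0.05.

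Under Data collection and monitoring the primary outcome appears twice. The short form is "The primary outcome of the study was a change in EtCO₂ over time". The next paragraph keeps the change over T0, T30 and T60 and adds "the comparison of these changes between the three analgesic groups".

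The analysis paragraph plans repeated-measures ANOVA within and between groups. For differences between groups, "one-way ANOVA with Tukey post hoc tests were employed". For change within a group, "Paired t tests were utilised for within-group comparisons between T0 and T60". None of these tests is tied to the sample size.

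The three arms, randomised 1:1:1, are dexketoprofen alone, tramadol alone, and the two combined. The cited data, as described, concern tramadol or oxycodone.

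**The concern.** A reader who wants to check 34 per group has alpha and power, but no effect size, SD, test, sidedness, correlation or target comparison. The rest of the text does not settle the target. The shorter wording of the primary outcome could be met by a change within an arm; the longer one requires a comparison between arms. Tests of both kinds are planned, and published changes after a drug could have supplied either a within-arm change or a contrast between two drugs.

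At stake is what the 80% means. Had the calculation been for a change within one arm, the same number of patients could have well under 80% power to separate the arms, and a non-significant difference between analgesics would be weaker evidence than the stated power suggests. In addition, the source as described does not cover dexketoprofen alone or the combination as such, and no reason is given for carrying its data over to those arms.

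**Working it through.** **Inputs from the document.** Alpha 0.05; power 80%; 34 per group, 102 in total; three arms, 1:1:1; time points T0, T30, T60. Not given: effect size, SD, test, sidedness, correlation.

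**Reproducing the plan's figure.** This is not possible, because the effect size and test are absent. One can only work backwards, asking which standardised effect gives about 80% power at 34 per arm under each candidate test. The calculations use noncentral t and F, two-sided for t unless stated. Effects are in units of the SD of the change.

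- *Paired t within one arm.* Noncentrality dz × √n. With dz = 0.50: 0.50 × √34 = 2.92 on 33 df, power 80.8%. At n = 33 it is 79.5%, so dz = 0.50 requires exactly 34.
- *Two-arm t on the change.* Noncentrality d × √(n/2). With d = 0.69: 0.69 × √17 = 2.84 on 66 df, power 80.0% (78.8% at n = 33).
- *Two-arm t, one-sided.* With d = 0.61: 0.61 × √17 = 2.52, power 80.1%.
- *Three-arm one-way ANOVA.* Noncentrality f² × N. With f = 0.312: 0.312² × 102 = 9.93 on 2 and 99 df, power 80.0%.
- *Repeated-measures group-by-time interaction*, sphericity assumed. Noncentrality f² × N × 3/(1 − ρ). With assumed ρ = 0.5 and f = 0.141: 0.141² × 102 × 3/0.5 = 12.2 on 4 and 198 df, power 80%. With ρ = 0.3 or 0.7 the corresponding f is 0.167 or 0.109.

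Five different calculations thus arrive at 34. That is unsurprising: any test gives any sample size for some effect.

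**Between-arm power at 34 per arm, by reading (illustrative).**

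- *Within-arm reading, dz = 0.50, one arm changing by 0.50 SD and the others not at all (both assumed).* Two-sample t: noncentrality 0.50 × √17 = 2.06, power 53%. Omnibus ANOVA: f = 0.50 × √2/3 = 0.236, power 54%. Tukey pairwise (critical value 2.379 on 99 df): 38%. If all arms change equally there is no difference to detect, and the omnibus test rejects at its 5% level. This reading therefore fixes no single between-arm power.
- *Two-sided two-arm reading, d = 0.69 to 0.70.* Unadjusted t: 80 to 81%. Tukey pairwise: 68 to 69%.
- *One-sided two-arm reading, d = 0.61.* Two-sided power 70%.
- *Three-arm reading, f = 0.312.* Omnibus power 80%.

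A split into about 53% or about 80% would be too tidy. The values spread from 38% to 81%, and each rests on an effect size that the document does not contain.

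**What the trial shows whichever reading is true.** With 34 complete patients per arm and a common SD of the change, the Tukey 95% interval for a pairwise difference has half-width 2.379 × √(2/34) = 2.379 × 0.2425 = 0.58 SD. That depends on the number of patients and the observed SD, not on the planning assumption.

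**The case for a change.** The strongest argument for acting is that the remedy is cheap and the ambiguity has consequences. Two or three sentences would show which comparison carries the 80%. Without them, a reader of a null result cannot tell a comparison planned at 80% from one at about half that. A citation does not answer this, because it does not say which contrast, SD or procedure was taken from the source. The exact match of 34 to a paired t test at the conventional medium effect of 0.50 makes a within-arm calculation a real possibility.

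Part of this stands. The inputs are missing, the number cannot be reproduced, and no reason is given for applying the cited data to the dexketoprofen and combination arms.

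The inference to low between-arm power does not stand. The text says the inputs came from published data, not from a conventional effect size. The two wordings of the primary outcome read as a summary and its expansion, and the fuller one includes the between-group comparison. A count per group with a three-arm total fits a between-group calculation at least as well. The paired t test uses only T0 and T60, whereas the primary outcome spans three time points, which makes it a weak candidate for the powered test. Tramadol is one arm and a component of another, so the borrowed data are not foreign to the trial, and borrowing an effect size from related drugs is ordinary practice. Still, none of this proves which comparison was powered.

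**Conclusion.** No change to the plan follows. This is a minor reporting omission: the document does not carry over the inputs to its sample-size calculation, so the power of the between-arm comparison cannot be determined from it. The figures of 38% to 81% are illustrations; they depend on assumed effects, on sidedness and on whether Tukey's adjustment is counted, and do not estimate this trial's power.

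Neither 34 per group nor 80% is shown to be wrong. The study is described in the past tense, from November 2024 to April 2025, so the sample size is no longer a decision to be made. Stating the inputs would record what was done and leave enrolment, tests, estimates and p values as they are. A null result is best read from the intervals that accompany the planned Tukey comparisons, about ±0.58 SD of the change with complete data and a common SD, and these need no planning assumption. Confidence is high that the inputs are absent; there is no basis for choosing among the readings.

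### Lactate is compared by ANOVA on unadjusted, untransformed change, and the normality check has no stated consequence; adjusting T60 lactate for T0 would use the collected data better

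*Combined protocol and SAP*

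**What the plan says.** Under Data collection and monitoring, blood gases are taken at T0 and T60 only, and lactate is one of five blood-gas secondary outcomes: "changes in arterial blood gas parameters (pH, bicarbonate, PaCO₂, lactate and" base deficit. Under Sample size and statistical analysis, the plan states that "The assessment of normality was conducted through histogram inspection" together with a Shapiro–Wilk test. No transformation, rank-based test, alternative summary or decision rule is tied to the result. "Continuous variables are presented as mean" with standard deviation, or as change over time. Blood-gas variables are analysed by repeated-measures ANOVA, between-group changes by one-way ANOVA with Tukey comparisons, and within-group changes by paired t tests. No covariate is named. The threshold is that "a p value of less than 0.05 was deemed to be significant". That lactate stays on its raw scale is inferred from the absence of any stated transformation.

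The sample size was set for EtCO₂, not lactate: with "80% power, 34 patients per group (102 in total) were required". The documents give no lactate mean, SD, skewness, T0–T60 correlation or expected effect.

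**The concern.** Two features of the plan matter for lactate.

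First, the analysis of change ignores how T60 depends on T0. Subtracting the whole baseline value adds baseline noise to the outcome unless the two values are very highly correlated. The repeated-measures ANOVA does not help: with two time points, its group-by-time test is the same F test as one-way ANOVA on the change.

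Second, a normality check without a consequence leaves two possibilities. Either lactate is analysed untransformed whatever the check shows, or the analyst picks a method after seeing the data. Lactate is a positive concentration, so right skew is plausible, and a few patients with high values could then dominate the variance of the raw change.

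At stake is the power of one secondary outcome. Lactate is the natural cross-check on EtCO₂, which the plan treats as a surrogate for tissue perfusion, so a missed lactate difference would weaken the interpretation of the primary result.

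**Working it through.** **The plan's own figure.** The 34 per group cannot be rebuilt, because no effect size, SD, correlation or test is given. Solving backwards at α = 0.05 and 80% power, it corresponds to f ≈ 0.312 for a three-group one-way ANOVA, or d ≈ 0.69 for a two-sample t test. It says nothing about lactate.

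**Inputs from the documents.** Three groups, 1:1:1; 34 per group (102 in total); α = 0.05; lactate at T0 and T60.

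**Assumed inputs.** T0 and T60 lactate are bivariate log-normal, with log-SD s = 0.4, 0.5 or 0.6 and log-scale correlation r = 0.5 or 0.7. One arm is 25% lower at T60 and the other two are unchanged.

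**Log-scale check by formula.** One arm differs by |ln 0.75| = 0.288, so the SD of the three group means is 0.288 × √2/3 = 0.136. The error SD is s√(2(1 − r)) for log change and s√(1 − r²) for log T60 adjusted for log T0. Then f = 0.136/SD and λ = 102f². At r = 0.5:

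| s | log change: SD, f, λ, power | adjusted log T60: SD, f, λ, power |
|---|---|---|
| 0.4 | 0.400, 0.339, 11.7, 87% | 0.346, 0.391, 15.6, 95% |
| 0.5 | 0.500, 0.271, 7.5, 67% | 0.433, 0.313, 10.0, 80% |
| 0.6 | 0.600, 0.226, 5.2, 51% | 0.520, 0.261, 6.9, 64% |

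**Simulation, including the raw scale.** With 10,000 trials per setting, the omnibus test at 5% and r = 0.5:

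| s | raw change (plan) | log change | raw T60 adjusted for T0 | log T60 adjusted for log T0 |
|---|---|---|---|---|
| 0.4 | 74% | 87% | 91% | 94% |
| 0.5 | 51% | 67% | 70% | 80% |
| 0.6 | 35% | 52% | 51% | 64% |

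The log columns agree with the formula to about a point.

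**Splitting the gain.** Baseline adjustment alone, on the raw scale, adds 91 − 74 = 17, 70 − 51 = 19 and 51 − 35 = 16 points. Logging on top of adjustment adds 94 − 91 = 3, 80 − 70 = 10 and 64 − 51 = 13. Most of the gain therefore comes from adjustment. The reason is visible in the variances: when T0 and T60 have equal variance and correlation ρ, the adjusted error variance is (1 − ρ²)σ² against 2(1 − ρ)σ² for change, a ratio of (1 + ρ)/2. At s = 0.5 and r = 0.5 the raw-scale correlation is (e^0.125 − 1)/(e^0.25 − 1) = 0.133/0.284 = 0.47, so the ratio is 0.73.

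**Scale alone, with r = 0.7 included.** At r = 0.7, raw change against log change is 92% v 98%, 72% v 89% and 52% v 75%. Over both correlations and repeated runs, the difference is about 5 to 23 points.

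**Sensitivity to the form of the effect.**
- One arm 33% higher instead of 25% lower: raw and log change differ by between nothing and about 7 points.
- Skewed levels with a symmetric additive change (for example median 1.5 mmol/L, shift 0.2, change SD 0.3): raw change keeps about 80% power and log change loses about 6 to 19 points. Raw adjusted T60 costs at most about 0.5 point against raw change.
- A common 10% fall in all arms on top of the 25% effect: raw-change power at r = 0.5 drops to 66%, 45% and 30%. Adjusted T60 is unaffected, because multiplying every T60 value by a constant leaves its F statistic unchanged.

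**Type I error.** About 4–5.5% for all methods.

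**The case against.** The strongest objection is that nothing here is invalid. Type I error is sound at 34 per arm. Lactate is one of five blood-gas secondary outcomes, and the trial was not powered for it. This stands, and it limits the point to efficiency.

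It is also fair that every lactate input is assumed. The entry criteria (ages 18–55, no haemodynamic instability, no chronic kidney disease) may narrow the upper tail, in which case a log-SD of 0.5 or 0.6 could be too high. At log-SD 0.3 raw change already has more than 90% power for a 25% reduction, so there is little to gain.

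A reader might infer that right skew by itself costs the planned analysis a substantial block of power, and that a log analysis keeps it. The documents do not support that. Skew alone is not enough: the loss on change scores also needs an effect proportional to level, is largest when that effect is a reduction, and needs at least moderate skew. The plan compares three active regimens and states no expected direction or form of lactate effect. If the change is additive, logging loses power. The log analysis also estimates a ratio rather than a difference in mmol/L, so the choice of scale is partly a choice of question.

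The case for baseline adjustment survives these objections. It does not depend on the scale, gains power under proportional reduction, and costs almost nothing under additive change.

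**Conclusion.** The point holds as an efficiency concern about one secondary outcome, and is minor. The plan compares lactate change without baseline adjustment, apparently untransformed, and its normality check leads nowhere. Under log-normal lactate, a 25% reduction in one arm and r = 0.5, adjusting T60 for T0 on the raw scale gains about 16 to 19 points at log-SD 0.4–0.6. The log-scale version gains 94 − 74 = 20, 80 − 51 = 29 and 64 − 35 = 29 points in total. These figures depend on assumptions that the documents neither give nor contradict. The direction of the adjustment gain is secure across the cases examined, apart from a cost of up to about half a point under additive change. The direction of the gain from logging is not. Making the log scale primary is a judgement that depends on whether a proportional effect is expected.

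**What to change.** Replace the one-way ANOVA on lactate change with a regression of T60 lactate on arm, with T0 lactate as covariate. State that Shapiro–Wilk will not be used to switch methods. Report the log-scale version (log T60 on arm and log T0, giving ratios of geometric means with 95% CIs) as a labelled sensitivity analysis, and add median with quartiles to the lactate summary. If the investigators expect a proportional effect and want the log scale as primary, they should say so with the reason.

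The text is written in the past tense. If lactate has already been analysed, the report should state which scale was used and why, and label the adjusted analyses as added afterwards.

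The cost is two or three sentences and a few lines of output. No new data are needed, and the only statistical price found is the half point under additive change.

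### Repeated-measures ANOVA discards any patient with a missing reading and no loss allowance is stated; a mixed model on the same data would use every reading, for a modest gain if readings are missing

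*Combined protocol and SAP*

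**What the plan says.** Under Data collection and monitoring, EtCO₂ and the vital signs are read at T0, T30 and T60. Blood gases have two time points: "Arterial blood-gas analysis was performed at T0 and T60". The primary outcome is the change in EtCO₂ over the three times, compared between the three arms.

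Under Sample size and statistical analysis:

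- The repeated variables "were subjected to analysis using repeated-measures ANOVA".
- Between-group changes are also compared by one-way ANOVA with Tukey tests, and T0 with T60 within groups by paired t tests.
- The sample size statement is that, with α = 0.05 "and 80% power, 34 patients per group (102 in total) were required". The effect size, SD and test family are not given; the inputs are attributed to a cited publication.

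The documents state no expected loss, missing-data rule or analysis set, and do not say how many patients were enrolled.

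**The concern.** Classical repeated-measures ANOVA needs a full set of readings from each patient. Someone with T0 and T30 but no T60 contributes nothing, although two of the three values were observed. Small gaps add up, because one missing reading of three is enough to remove the patient.

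Two things could follow. First, 34 per group is given as the number required, with no stated inflation, so lost patients would come off the 80% power. Second, readings could be missing for reasons tied to response, such as leaving early after pain relief or declining a second arterial puncture. If that happened unequally across arms, the patients left would not be a fair comparison. These reasons are plausible for an emergency department, but the documents do not report them.

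**Working it through.** **Inputs from the plan.** α = 0.05 (two-sided, or an F test, assumed), power 80%, 34 per arm, three arms, three EtCO₂ readings.

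**Assumed, because the plan is silent.** Loss rates; correlations of 0.5 (T0–T30), 0.4 (T0–T60) and 0.8 (T30–T60); equal SD at each time.

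**1. The plan's own figure.** The 34 per arm cannot be reproduced forward without an effect size. Solving backwards for the effect that gives 80% power at 34 per arm (n per arm, N = 3n in total):

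- Two-sample t test, df = 2n − 2, noncentrality d√(n/2): d = 0.690.
- One-way ANOVA, df = 2 and N − 3, noncentrality f²N: f = 0.312.
- Group-by-time interaction, df = 4 and 2(N − 3), noncentrality 3f²N/(1 − ρ) with ρ = 0.5 assumed: f = 0.1413.

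A t test with d = 0.70 also returns 34 after rounding up, and is close to the most favourable effect for which 34 is still the minimum.

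**2. Power with fewer complete patients, effects held fixed.**

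| Complete per arm | t, d = 0.690 | One-way F, f = 0.312 | Interaction, f = 0.1413 | t, d = 0.70 |
|---|---|---|---|---|
| 34 | 80.0% | 80.0% | 80.0% | 81.2% |
| 33 | 78.8% | 78.7% | 78.6% | 80.0% |
| 32 | 77.5% | 77.3% | 77.1% | 78.7% |
| 31 | 76.2% | 75.8% | 75.6% | 77.4% |
| 28 | 71.7% | 71.1% | 70.5% | 73.0% |

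**3. How gaps compound.** If each of three readings is missing independently with probability q, the share of patients dropped is 1 − (1 − q)³. For q = 2%, 3% and 5% this is 5.9%, 8.7% and 14.3%, leaving about 32, 31 and 29 per arm.

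**4. Precision with 10% of T60 missing at random** (34 × 0.9 = 30.6 complete per arm). The T0-to-T60 change has variance 2 − 2 × 0.4 = 1.2 SD². The SE of a difference between two arms is:

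- Full data: √(2 × 1.2/34) = 0.266 SD.
- Complete cases: √(2 × 1.2/30.6) = 0.280 SD.
- Mixed model using T0 and T30: these correlations leave a T60 residual variance of 1 − 0.8² = 0.36, so √[2(0.84/34 + 0.36/30.6)] = 0.270 SD.
- Mixed model with T0 only, as for blood gases: the residual variance is 1 − 0.4² = 0.84, so √[2(0.36/34 + 0.84/30.6)] = 0.276 SD.

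The model recovers (0.280 − 0.270)/(0.280 − 0.266), about 70% of the lost precision, with three readings. With two readings it recovers (0.280 − 0.276)/(0.280 − 0.266), about 30%.

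**5. Bias when T60 loss depends on T30.** Take a logit slope of 1 per SD and no true arm difference. With these correlations, the mean change among patients still observed is (0.8 − 0.5) times their mean T30. By numerical integration, mean T30 among the observed is −0.029, −0.091 and −0.173 SD at 3%, 10% and 20% loss. The mean change is therefore −0.009, −0.027 and −0.052 SD.

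- 20% arm against 3% arm: −0.052 − (−0.009) = −0.043 SD. Simulations of the same scenario gave −0.04 to −0.05 SD.
- Equal loss in both arms: the two terms cancel and the bias is zero.
- Mixed model: about zero in either case, because loss that depends on T30 leaves the regression of T60 on the earlier readings unchanged.

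**The case against.** The strongest reply is that no missing reading is documented. Follow-up lasts 60 minutes in one department, loss may be negligible, and at zero loss the two methods lead to essentially the same conclusions. That stands: the benefit is conditional.

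The plan's one-way ANOVA of changes also softens the point. For a T0-to-T60 comparison it needs two readings, so a missing T30 alone removes nobody. A missing T60 still does.

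The sizes are modest too. A bias of −0.05 SD is 0.05/0.282 = 0.18 of a standard error (0.282 being the simulated complete-case SE) and would move a 5% test to about 5.4%. The power figures rest on back-solved effects, because the plan's own effect size is not stated.

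A reader might go further and infer that the trial had no spare patients, was underpowered, or has a biased arm comparison. The documents support none of these. They call 34 per group the required number; they do not call it an enrolment cap or the number recruited, and they do not exclude an allowance already built in. What can be said is that none is stated.

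What remains is that the plan has no rule for incomplete patients, and its named repeated-measures method discards them when a simple alternative does not.

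**Conclusion.** The point holds as an inexpensive improvement, not as an error that invalidates the plan. If two or three patients per arm were incomplete, power would be about 77–79% or 76–77% instead of 80%. Bias in the T0-to-T60 change would be about −0.04 to −0.05 SD under loss of 3%/10%/20% by arm that depends on T30, and essentially zero if loss is equal across arms. With complete data nothing changes.

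These sizes rest on back-solved effects, assumed correlations and assumed loss rates. The mixed model's advantage is clearest for EtCO₂ and the other three-time-point variables, and depends on how well T30 predicts T60. It is limited for blood gases. The model does not correct loss that depends on the unobserved T60 value itself.

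**What to change.** - For EtCO₂ and the other variables read at T0, T30 and T60, replace repeated-measures ANOVA with a REML linear mixed model: fixed effects of arm, time and arm-by-time, unstructured covariance, and all available readings from every randomised patient in the assigned arm.
- Take the between-arm change contrasts from that model with a multiplicity adjustment, in place of the separate one-way ANOVA with Tukey tests.
- The same model may be used for T0 and T60 blood gases, with a note that it recovers only part of the lost precision.
- Report the number of patients contributing at each time point, by arm, so that readers can judge how much loss there was.

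The cost is revised analysis wording, a different SPSS procedure and a missing-at-random assumption that should be stated. No further patients or data are needed, which matters because the study is described in the past tense.
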